Appendix 1.

STUDY SYNOPSIS

- **Title** Effects of orally administered Beta-glucan on leukocyte function in humans, a pilot study
- **Indication** Immune stimulatory therapies
- **Objectives** *Primary objective:*

The primary objective of the study is to evaluate the effects of orally administered Beta-glucan on human leukocyte function. The effects of Beta-glucan will be determined by measuring the *ex vivo* responsiveness of leukocytes to various inflammatory stimuli, as well as phagocytosis and killing of pathogens, as markers of the antimicrobial response, and the pathogen phagocytosis and killing capacity of leukocytes. The primary outcome measure is the TNF- α secretion by *ex vivo* LPS-stimulated peripheral blood mononuclear cells (PBMCs).

Secondary Objective(s): There are 6 secondary objectives:

- 1. To determine the production of other cytokines (TNF- α , IL-6, IL-10, IL-1 β , IL-17, IL-22, Interferon (IFN)- γ) by leukocytes *ex vivo* stimulated with various stimuli (including LPS, Pam3Cys, Mycobacterium tuberculosis, Poly(I:C), Candida albicans, staphylococcus aureus).
- 2. To determine the absorbance of orally administered Beta-glucan into the blood compartment, measured by ELISA.
- 3. To determine the effects of Beta-glucan on changes in phenotype and gene expression caused by mechanisms other than changes in the underlying DNA sequence (epigenetic modifications).
- 4. To determine the effects of Beta-glucan on transcriptional pathways (by use of microarrays) with focus on inflammatory pathways.
- 5. To determine the effects of Beta-glucan on the leukocyte capacity to phagocytose and kill the fungal pathogen *Candida albicans*.
- 6. To determine the effects of Beta-glucan on faecal microbiota
- **Study design** An open-label, intervention pilot-study in healthy human volunteers.
- **Sample size** 15 healthy volunteers.

Eligibility criteria Inclusion criteria

- Written informed consent
- Age≥18
- Healthy

Exclusion criteria

- Subjects with a history of allergy or intolerance to Beta-glucan
- Use of any medication
- Participation in a drug trial or donation of blood 3 months prior to Beta-glucan administration
- Use of antibiotics, norit, laxatives (up till 6 months prior to inclusion), cholestyramine, acid burn inhibitors or immune

suppressive agents (up till 3 months prior to inclusion), and preand probiotics (up till 1 month prior to inclusion).

Drugs and dosage Commercial available Beta-glucan derived from bakers yeast (S. Cerevisiae): Glucan #300® produced by Transferpoint, Columbia, United States. 2 capsules of 500mg Glucan #300®, daily, for seven days.

Route of administration Oral administration.

Procedures 10 Healthy volunteers will take Beta-glucan 1000 mg daily for seven days, 5 other healthy volunteers will serve as a control group and do not have to take Beta-glucan. The *ex-vivo* responsiveness of leukocytes to various inflammatory stimuli, peripheral blood mRNA expression of genes related to the immune response, epigenetic modifications, the leukocyte capacity to phagocytose and kill the fungal pathogen *Candida albicans*, blood levels of Beta-glucan, and faecal microbiota will be analyzed on different timepoints.

Statistical analysis Descriptive statistics.

1 INTRODUCTION AND RATIONALE

For centuries mankind has tried to improve their defense mechanisms against invading pathogens. The innate immunity is the first line of defense after the body's mechanical barriers. In many pathological situations that occur naturally (for example sepsis) or iatrogenic (for example chemotherapy), enhancement of the immune response is desirable. However, immune stimulating therapies are scarce, expensive, and often have undesirable side-effects.

[figure not shown]
The immunostimulatory properties of mushrooms have been recognized for centuries, and "medicinal" mushrooms are still widely used in alternative medicine all over the world. Although a number of fungal components have been implicated in these properties, Beta-glucans have attracted the most attention [1]. Numerous *in vitro* and animal studies have demonstrated immunomodulatory and anticancer effects of Beta-glucans. Moreover, recent molecular immunological studies have elucidated the immunological mechanisms behind recognition of glucans by immune cells and subsequent alterations of cellular responses [2]. However, although Beta-glucans are widely used as a health food supplement, their immunomodulatory effects after administration in humans have not yet been determined.

Structure

Structurally, all Beta-glucans are glucose polymers linked together by a 1-3 linear Betaglycosidic chain core that differ from each other by their length and branching configuration [2, 3]. The branches derived from the glycosidic chain core are either 1-4 or 1-6 glycosidic chains that appear to be dependent on the source. Beta-glucans can not only be isolated from cell walls of mushrooms and yeasts, but also from cell walls of other fungi, bacteria, algae, and cereal grains [4]. Their activity is influenced by their degree of branching, size, and their molecular structure [5, 6], but also by the purity of the preparation [6]. The most active Betaglucans have a common structure: a main chain consisting of (1-3)-linked Beta-D glucopyranosyl units along which are randomly dispersed single Beta-D-glucopyranosyl units attached by 1-6 or 1-4 linkages [4] (Figure 1).

[figure not shown]
Immunity

Beta-glucans are not found in animals and are considered to be classic pathogen-associated molecular patterns (PAMPs) [7] which are recognized by the innate immune system of vertebrates, as well as invertebrates. The ability of the immune system to recognize and respond to PAMPs is dependent on pattern recognition receptors (PRRs) that have been identified on various human immune cells including monocytes, macrophages, neutrophils, and NK cells. To date, there have been four different Beta-glucan PRRs described including complement receptor 3 (CR3) [8], scavenger receptors [9], lactosylceramide [10], and most recently dectin 1 [11]. By binding to these PRRs, Beta-glucans are potent activators of the innate immune system and they are most well known for their ability to stimulate the immune system and boost resistance to various viral, bacterial, protozoan, and fungal diseases, as well as to promote antitumor activity. However, up till now, these effects have only been established *in vitro* and in animal models.

cereal *β*-glucan

Polymer of β -(1-4)-D-glycopyranosyl units separated by single β -(1-3)-D-glycopyranosyl units.

yeast β-glucan

Polymer of β -(1-3)-D-glycopyranosyl units with branching at β -(1-6)-D-glycopyranosyl units

β-Glucan type	Structure	Description
Bacterial		Linear β1,3 glucan (i.e. Curdlan)
Fungal		Short β 1,6 branched, β 1,3 glucan (i.e. Schizophyllan)
Yeast		Long β1,6 branched, β1,3-glucan (i.e. WGP β-glucan, Betafectin™)
Cereal		Linear β1,3/β1,4-glucan (i.e oat, barley, rye)

Figure 1. Structure of cereal and yeast Beta-glucan and scheme of various Beta-glucan sources. Adapted from Volman et al. [6].

In vitro studies

Beta-glucans enhance the functional activity of human macrophages and activate antimicrobial activity of mononuclear cells and neutrophils *in vitro* [4, 5, 12]. This enhanced immune response is accomplished by increases in pro-inflammatory cytokine and chemokine production [13-18] and oxidative burst [5, 19]. Moreover, besides leukocytes, also epithelial cells can respond to Beta-Glucans [20].

Animal studies

Next to *in-vitro* work, animal studies have been conducted to evaluate the immunomodulatory effects of Beta-glucans. Several studies have been carried out with isolated leukocytes from animals that were treated with Beta-glucans supplied via various routes. Subsequently, these isolated cells were challenged with LPS or pathogens (*ex vivo*). In general, *ex vivo* stimulated leukocytes from Beta-glucan-treated animals showed increases in pro-inflammatory cytokine production [21], oxidative burst [22], and chemotaxis [23]. Furthermore, *in vivo* studies in mice and rats have shown that intravenous or intraperitoneal Beta-glucan administration improves survival compared with control animals after challenge with fungal (Candida albicans), gram-positive (Staphylococcus. aureus), and gram-negative (Escherichia coli) pathogens [24-26].

Human in vivo evidence

Although the ability of Beta-glucan to enhance host resistance in rodents is well established, there are very few studies to support these effects in humans *in vivo*. Two clinical studies reported that intravenously administered Beta-glucan increased CD4 levels of HIV positive patients with low CD4 levels [27, 28]. It has also been reported that intravenously administered Beta-glucan resulted in decreased infection incidence, need

for antibiotics, shortened intensive care unit length stay, and ultimately improved survival compared to placebo in high-risk surgical patients [29-31]. Furthermore, it was recently reported that oral Beta-glucan derived from *S. cerevisiae* results in enhanced expression of surface molecules associated with monocyte activation (Fas/APO-1, CD95) in patients with advanced breast cancer [32]. However, none of these studies evaluated the effects of Beta-glucan on human leukocyte function in terms of cytokine production or possible reversal of immunoparalysis.

Routes of administration

Beta-glucan is commonly administered parentally in animals and humans, while oral administration is not frequently used. This is probably due to the fact that most studies have used a Beta-glucan derived from yeast (lentinan), which is only available for parenteral use. However, in recent years a number of reports have shown that enteral administration of Beta-glucans from different sources also results in biological effects: humoral and cellular immune responses of orally administered Beta-glucan were demonstrated in animals [21], as well as enhanced resistance to bacterial and parasitic infections [33-37]. As mentioned above, in humans it was recently reported that oral Beta-glucan derived from *S. cerevisiae* results in enhanced breast cancer [32]. Moreover, systemic administration is not preferable as Beta-glucans can cause pain, granuloma's, anaphylatoxins, higher sensitivity to endotoxins, and development of micro-embolism [4]. These side-effects can be avoided by oral administration [38]. Furthermore, oral formulations of Beta-glucan are generally less expensive than their parental counterparts.

Based on these data, oral administration of Beta-glucan appears, from an immunological point-of-view, as effective as parenteral administration, is generally less expensive, and is thought to have fewer side-effects.

Study proposal

In the present application we propose to conduct a pilot study to investigate the effects of a commonly available and orally administered Beta-glucan on the innate immune response of leukocytes in humans and on faecal microbiota.

Research questions:

- 1. Does orally administered Beta-glucan modulate the *ex vivo* responsiveness of leukocytes to various inflammatory stimuli (which represents a surrogate marker for the antimicrobial response)?
- 2. Is orally administered Beta-glucan detectable in the blood compartment?
- 3. Does orally administered Beta-glucan induce changes in phenotype or gene expression caused by mechanisms other than changes in the underlying DNA sequence in leukocytes (determined by epigenetics)?
- 4. Does orally administered Beta-glucan affect inflammatory transcriptional pathways in leukocytes (determined by microarray)?
- 5. Does administration of Beta-glucan improve the capacity of leukocytes to phagocytose and kill pathogens such as the fungus *Candida albicans*?
- 6. To what extend does administration of Beta-glucan affect the composition of faecal microbiota?

2 OBJECTIVES

Primary objective:

The primary objective of the study is to evaluate the systemic effects of orally administered Beta-glucan on innate immune responses of leukocytes. The effects of Beta-glucan will be determined by measuring the *ex vivo* responsiveness of leukocytes to various inflammatory stimuli as a surrogate marker of the antimicrobial response, and the pathogen phagocytosis and killing capacity of leukocytes. The primary outcome measure is the TNF- α secretion by *ex vivo* LPS-stimulated peripheral blood mononuclear cells (PBMCs).

Secondary Objective(s): There are 6 secondary objectives:

- 1. To determine the production of other cytokines (IL-1Ra, IL-6, IL-8, IL-10, Interferon (IFN)- γ) by leukocytes *ex vivo* stimulated with various stimuli (including LPS, peptidoglycan, *Candida albicans*).
- 2. To determine the penetration of orally administered Beta-glucan into the blood compartment, measured by ELISA.
- 3. To determine the effects of Beta-glucan on changes in phenotype and gene expression caused by mechanisms other than changes in the underlying DNA sequence (epigenetic modifications).
- 4. To determine the effects of Beta-glucan on transcriptional pathways (by use of microarrays) with focus on inflammatory pathways.
- 5. To determine the effects of Beta-glucan on the leukocyte capacity to phagocytose and kill the fungal pathogen *Candida albicans*.
- 6. To determine the effects of Beta-glucan on faecal microbiota.

3 STUDY DESIGN

An open-label, intervention pilot-study in 15 healthy human volunteers. In this pilot study, we will enrol 10 subjects who will take Beta-glucan daily for seven days, and 5 subjects who will serve as control group and do not have to take Beta-glucan but who will be analyzed at the same time points as the subjects in the Beta-glucan group.

4 STUDY POPULATION

4.1 **Population (base):**

The study population consists of 15 healthy male volunteers. Before inclusion subjects must meet all inclusion criteria and none of the exclusion criteria. Recruitment of healthy volunteers will take place by placement of posters in the medical faculty and several other faculties and locations on the campus of the Radboud University Nijmegen.

4.2 Inclusion criteria

- Written informed consent
- Age ≥18
- Healthy males

4.3 Exclusion criteria

- Subjects with a history of allergy or intolerance to Beta-glucan
- Use of any medication
- Participation in a drug trial or donation of blood 3 months prior to Beta-glucan administration
- Use of antibiotics, norit, laxatives (up till 6 months prior to inclusion), cholestyramine, acid burn inhibitors or immune suppressive agents (up till 3 months prior to inclusion), and pre- and probiotics (up till 1 month prior to inclusion).

4.4 Sample size calculation

The present study is a safety and proof-of-principle pilot study. A power calculation is not warranted, as the extent (and related clinical relevance) of modulation of the innate immune response *in vivo* by the intervention is currently unknown.

5 TREATMENT OF SUBJECTS

5.1 Investigational product/treatment

In this pilot-study we will use a Beta-glucan that is commonly available as a health food supplement derived from bakers yeast (*S. cerevisiae*) and that has been used *in vivo* in mice with strong immune modulating properties and no observed toxicity [39, 40] (Glucan #300®, produced by transferpoint, Columbia, United States). Dosage is based on the dosage recommended by the manufacturer.

5.2 Use of co-intervention

Not applicable

5.3 Escape medication

Not applicable

6 INVESTIGATIONAL MEDICINAL PRODUCT

6.1 Name and description of investigational medicinal product

Commercial available Beta-glucan derived from bakers yeast (*S. cerevisiae*): Glucan #300 produced by Biothera (Eagan, Minnesota, USA) for Transferpoint (Columbia, USA).

6.2 Summary of findings from non-clinical studies

Summary of findings from non-clinical studies are described in the introduction section.

6.3 Summary of findings from clinical studies

Summary of findings from clinical studies are described in the introduction section.

6.4 Summary of known and potential risks and benefits

Purified polysaccharidic immunomodulators distinguish themselves by very low toxicity (e.g., for mice lentinan has a $LD_{50} > 1600 \text{mg/kg}$ [41]). Moreover, Beta-glucans are commonly available as health food supplements and are considered safe and non-toxic, with the classification of "GRAS" (Generally recognized as safe) by the FDA as a dietary food additive supplement [42] and by the Dutch Medicines Evaluation Board (MEB) [43] (see summary of product characteristics).

6.5 Description and justification of route of administration and dosage

Oral administration is a regular route of administration (see Summary of Product Characteristics). Dosages are based on the dosage recommended by the manufacturer.

6.6 Dosages, dosage modifications and method of administration

Oral administration is a regular route of administration (see Summary of Product Characteristics). Dosages are based on the dosage recommended by the manufacturer.

6.7 Preparation and labeling of Investigational Medicinal Product

Beta-Glucan is purchased directly from manufacturer and directly delivered to the researcher in containers containing 60 capsules. The capsules will be distributed to the subjects on the first study day in, by the researcher pre-filled, medicine boxes.

6.8 Drug accountability

The products are transported to the intensive care research unit and stored there under GMP conditions.

7 METHODS

7.1 Study parameters/endpoints

7.1.1 Main study parameter/endpoints

The primary objective of the study is to evaluate the systemic effects of orally administered Beta-glucan on innate immune responses of leukocytes. The effects of Beta-glucan will be determined by measuring the *ex-vivo* responsiveness of leukocytes to various inflammatory stimuli as a marker for the antimicrobial response. The primary outcome measure is the TNF- α secretion by *ex vivo* LPS-stimulated peripheral blood mononuclear cells (PBMC's).

7.1.2 Secondary study parameters/endpoints

- production of other cytokines (TNF-, αIL-6, IL-10, IL-1β, IL-17, IL-22, Interferon (IFN)-γ) by leukocytes *ex vivo* stimulated with various stimuli (including LPS, Pam3Cys, Mycobacterium tuberculosis, Poly(I:C), Candida albicans, staphylococcus aureus)
- the absorbance of orally administered Beta-glucan into the blood compartment, measured by ELISA.
- transcriptional pathways (by use of microarrays) with focus on inflammatory pathways.
- changes in phenotype and gene expression caused by mechanisms other than changes in the underlying DNA sequence (epigenetic modifications)
- the leukocyte capacity to phagocytose and kill the fungal pathogen *Candida albicans* (antifungal activity).
- composition of faecal microbiota

7.1.3 Other study parameters Not applicable

7.2 Randomisation, blinding and treatment allocation

We will use a open-label design in which subjects will be randomized to the Beta-glucan or control group by the opening of sealed envelopes.

7.3 Study procedures

Healthy volunteers who meet all inclusion criteria, none of the exclusion criteria and have given informed consent to participate in the study will be randomized to the Beta-glucan or the control group. The subjects in the Beta-glucan group will take Beta-glucan 1000 mg daily for 7 days, the subjects in the control group won't have to take Beta-glucan but will otherwise follow the same timecourse as the Beta-glucan treated subjects. Before, and 3, 6, and 24 hours after the first Beta-glucan ingestion (day 0), before, and 3 and 6 hours after the 7th ingestion of Beta-glucan (day 6), and on day 21 subjects have to come to the research room of the intensive care research unit for blood sampling (see appendix 1 for flowchart). On the first day of Beta-glucan ingestion we want to determine the immediate effects of oral Beta-glucan on leukocyte function, and if possible establish a plasma concentration – response curve. After 7 days of Beta-glucan ingestion we want to do the same measurements to determine

whether there is an additive effect of repetitive Beta-glucan intake. After 3 weeks we want to determine whether short-term intake of Beta-glucan results in prolonged immunological effects. Before the first intake of Beta-glucan subjects have to hand in 2 faecal samples collected within 48 hours prior to Beta-glucan intake, and one faecal sample collected within 24 hours prior to days 6 and 21. Throughout the studyperiod, subjects will document their consumption of Beta-glucan containing foods in an "eat-diary" (Appendix 2), with a maximalization of the amount of consumed Beta-glucan containing foods in order to minimize the inter-variability caused by variation in diet (Appendix 2).

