7.3.1 Time course

Baseline Evaluation (day 0):

• 2 faecal samples collected within 48 hours prior to Beta-glucan intake for analysis of microbiota. Blood sampling prior to Beta-glucan intake for immunological analysis (cytokine production of leukocytes stimulated *ex vivo* with various stimuli), for analysis of peripheral blood mRNA expression of genes related to the immune response, epigenetic modifications, levels of Beta-glucan, and phagocytosis and killing of *C. albicans*.

3 hours after the first Beta-glucan intake (day 0 + 3 hours):

• Blood sampling for immunological analysis (cytokine production of leukocytes stimulated *ex vivo* with various stimuli), for analysis of peripheral blood mRNA expression of genes related to the immune response, and levels of Beta-glucan.

6 hours after the first Beta-glucan intake (day 0 + 6 hours):

• Blood sampling for immunological analysis (cytokine production of leukocytes stimulated *ex vivo* with various stimuli), for analysis of peripheral blood mRNA expression of genes related to the immune response and levels of Beta-glucan.

24 hours after the first Beta-glucan intake (day 1):

• Blood sampling for immunological analysis (cytokine production of leukocytes stimulated *ex vivo* with various stimuli), for analysis of peripheral blood mRNA expression of genes related to the immune response and levels of Beta-glucan.

Days 0-5:

• Daily intake of 1000mg Beta-glucan

Day 6:

- 1 faecal sample collected within 24 hours prior to the last Beta-glucan intake for analysis of microbiota. Blood sampling prior to the last Beta-glucan intake for immunological analysis (cytokine production of leukocytes stimulated *ex vivo* with various stimuli), for analysis of peripheral blood mRNA expression of genes related to the immune response, epigenetic modifications, levels of Beta-glucan, and phagocytosis and killing of *C. albicans*.
- Registration of any adverse experience. This includes any intercurrent illness that may arise during therapy.

3 hours after the last Beta-glucan intake (day 6 + 3 hours):

• Blood sampling for immunological analysis (cytokine production of leukocytes stimulated *ex vivo* with various stimuli), for analysis of peripheral blood mRNA expression of genes related to the immune response, levels of Beta-glucan.

6 hours after the last Beta-glucan intake (day 6 + 6 hours):

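### Section 7.3 sets day 6 the aim of detecting an additive effect of repeated intake, but with no single-dose follow-up a first-dose effect emerging after 24 h cannot be told from later doses

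*Protocol*

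**What the plan says.** The relevant text is in sections 3, 7.3 and 7.3.1 of the protocol.

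- **Aim of day 6.** Section 7.3 wants the first-day measurements to show immediate effects. It wants the same measurements after the week of intake to determine "whether there is an additive effect of repetitive Beta-glucan intake".
- **Arms.** Section 3: "we will enrol 10 subjects who will take Beta-glucan daily for seven days, and 5 subjects who will serve as control group". Section 7.3: "The subjects in the Beta-glucan group will take Beta-glucan 1000 mg daily for 7 days", while "the subjects in the control group won't have to take Beta-glucan but will otherwise follow the same timecourse". There is no third arm.
- **Sampling.** Blood is drawn before and 3, 6 and 24 h after the first intake, before and 3 and 6 h after the seventh, and on day 21. The day 6 entry of section 7.3.1 has "Blood sampling prior to the last Beta-glucan intake for immunological analysis".
- **What is measured when (section 7.3.1).** Cytokine production, mRNA expression and Beta-glucan levels are scheduled at all eight points. Killing of *C. albicans* is scheduled only before the first dose and before the day 6 dose. Epigenetic analysis is scheduled at those two points and on day 21.
- **Lasting effects.** Section 7.3 also says: "After 3 weeks we want to determine whether short-term intake of Beta-glucan results in prolonged immunological effects".
- **Analysis.** Section 8.2 gives paired tests, repeated-measures ANOVA and a 0.05 threshold. It ties none of them to additivity.

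**The concern.** To say that repeated intake adds something, one must know what the first intake alone would have produced by day 6. The trial never observes this. The treated-minus-control difference on day 6 is the late effect of the first dose plus whatever later doses contribute, and only the sum is visible. The untreated arm removes time trend, repeat-sampling effects and assay drift, but says nothing about how the sum divides.

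A difference on day 6 could therefore be reported as support for repeated intake when a slow response to the first dose would explain it equally well. Whether repetition adds effect bears on the regimen of later studies. A larger sample would not help, and an analysis plan could not repair it, because the missing quantity is not in the data.

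**Working it through.** The protocol gives no effect size, SD or power (section 4.4), so there is no figure to reproduce. The check is one of identifiability, followed by an illustration of size.

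**1. Identifiability.** Take the cell means at the eight sampling times (0, 3, 6, 24 h; day 6 pre-dose, +3 h, +6 h; day 21). Parameters:

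- 8 time effects, common to both arms;
- 7 first-dose effects f(t), one per post-dose time;
- 4 later-dose effects g(t), at day 6 pre-dose, +3 h, +6 h and day 21.

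That makes 8 + 7 + 4 = 19. The 24 h sample is taken to precede the second intake, which the protocol does not state.

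- As planned (untreated and seven-dose arms): 16 cell means, rank 15, so 19 − 15 = 4 parameters cannot be estimated. At each of the last four times, f and g enter only as f + g.
- With a purely hypothetical single-dose arm at the same times: rank 19 of 19. This shows what information is missing. It is not a proposal.

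**2. Numerical example (assumed effects).** Suppose each intake adds 10 units lasting 7 days. The treated-minus-control means at the eight times are 0, 10, 10, 10, 60, 70, 70, 0. At day 6 pre-dose six intakes contribute (days 0 to 5): 6 × 10 = 60. After the seventh: 7 × 10 = 70. A first-dose-only response that rises after 24 h can take the same eight values, and the trial would return the same data under either explanation.

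**3. What the 24 h sample contributes.** The between-arm contrast of day 6 pre-dose minus 24 h equals [f(day 6) − f(24 h)] + g(day 6). If the first-dose effect is stable, so that f(day 6) = f(24 h), and later doses add nothing, this is zero and a test of it rejects at its nominal 5%. The sample thus protects against a stable lasting effect where it is measured: cytokines (including the primary TNF-α), mRNA and Beta-glucan levels. It does not protect against an effect that appears or grows after 24 h. For killing and epigenetics no sample lies between the first dose and day 6, so there is no single-dose reference at all.

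**4. Illustrative size.** Assume that only the first dose acts, that its effect emerges after 24 h, that it shifts day 6 by δ SDs of the within-subject change, and that any significant day 6 shift is called additivity. With two-sided α = 0.05 (the protocol does not state sidedness):

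- Paired, n = 10: noncentrality δ√10, 9 df, critical value 2.262.
- 10 v 5: noncentrality δ√(10 × 5/15) = 1.826δ, 13 df, critical value 2.160.

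| δ | Paired, n = 10 | 10 v 5 |
|---|---|---|
| 0.3 | 14% | 8% |
| 0.5 | 29% | 14% |
| 0.8 | 62% | 27% |
| 1.0 | 80% | 39% |

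These are t-test powers at chosen shifts. The confounding in step 1 does not depend on them.

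**The case against.** The strongest replies, and what stands of each:

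- **The protocol asks a question and claims no result.** This stands. A reader might infer that section 7.3 promises additivity or that additivity would be declared. The text says only that the investigators want to determine whether it exists, and no rule for declaring it is given. What remains is that the design cannot answer the question as put.
- **The 24 h sample separates one dose from several.** This stands in part. A reader might infer that any lasting first-dose effect would pass for additivity. For cytokines, mRNA and Beta-glucan levels that is wrong, since a stable effect would already be present at 24 h. Section 7.3.2 omits this point from its list of immunological time-points, but its count of eight draws requires it. Effects emerging after 24 h, and the two endpoints not measured then, are not covered. The day 21 and epigenetic aims make persistence plausible but do not in themselves suggest late onset.
- **The error rates are invented.** The shifts and the decision rule are indeed assumptions. The 80% is the top of a range, not a property of this trial.
- **Six intakes or seven.** A reader might see a contradiction between a day 6 pre-dose sample that follows six intakes and the description of day 6 as coming after seven days. There is none: section 7.3 itself places the day 6 draws before and after the seventh ingestion.
- **Contrasts belong in an analysis plan.** Their absence alone would be no finding. The point here is an aim, fixed in the protocol, that no contrast can meet.
- **It is a side question in a pilot.** This stands. Additivity is not among the objectives, endpoints or research questions.

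**Conclusion.** The point holds in a limited form and is minor. From day 6 onward, the contribution of later doses is fully confounded with any first-dose effect that emerges or grows after 24 h: four effects cannot be estimated under the planned design. For killing and epigenetics there is no single-dose reference of any kind before day 6.

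This rests only on the two-arm structure and the sampling schedule, plus the assumption that the 24 h blood is drawn before the second intake. If it were drawn after, the protection described for cytokines, mRNA and Beta-glucan levels would be weaker. The range of 14% to 80% (paired) or 8% to 39% (10 v 5) depends on assumed shifts of 0.3 to 1.0 SD and an assumed reading rule, and should be quoted only as illustration.

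A reader might infer that the primary result is compromised. It is not: LPS-stimulated TNF-α in treated versus control subjects remains estimable as the effect of the course.

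**What to change.** In section 7.3, replace the additive aim by contrasts compared between arms:

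1. **Effect of the course so far:** day 6 pre-dose minus day 0 pre-dose, reported as the effect after six daily intakes and not divided into delayed and added parts. Where a 24 h sample exists, give day 6 pre-dose minus 24 h as a supporting contrast.
2. **Change in acute response:** (day 6 +3 h or +6 h minus day 6 pre-dose) minus (day 0 +3 h or +6 h minus day 0 pre-dose).

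Add a sentence that a day 6 difference could reflect a delayed effect of the first dose, so that additivity of repeated intake cannot be concluded from it, and that killing and epigenetics have no single-dose reference. State whether the 24 h blood precedes the second intake.

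Dosing, sampling and sample size stay as they are. The cost is a few sentences and a weaker stated claim.
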